8.5.7.7 Follow-up of Adverse Events

Any AE will be followed (up to a maximum of 30 days after dosing with study drug) to a satisfactory resolution or until the Investigator deems the event to be chronic or not clinically significant or the subject to be stable. All findings relevant to the final outcome of an AE must be reported in the subject's medical record and recorded on the appropriate CRF.

8.5.8 Reporting Pregnancies

If a female subject or the female partner of a male subject becomes pregnant during the course of the study, or within 30 days after the last dose of study drug/placebo, the Investigator must report the pregnancy to Target Health LLC. within 24 hours of being notified. Target Health LLC. will then forward the Exposure in Utero form to the Investigator for completion. The Investigator must obtain consent to collect pregnancy information from the female subject or female partner of a male subject (including the outcome of the pregnancy and any SAEs, if applicable).

A subject becoming pregnant while on study drug will immediately be withdrawn from further dosing but will continue to be followed throughout the duration of the study.

The subject or partner should be followed by the Investigator until completion of the pregnancy, whenever possible. If the pregnancy ends for any reason before the anticipated date, the Investigator should notify Target Health LLC. At the completion of the pregnancy, the Investigator will document the outcome of the pregnancy. If the outcome of the pregnancy meets the criteria for immediate classification as an SAE (i.e., postpartum complication, spontaneous abortion, stillbirth, neonatal death, or congenital anomaly), the Investigator should follow the procedures for reporting an SAE.

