In Part B, eligible subjects, in 3 cohorts, will be randomized on Day 1 (pre-dose) to placebo (n=2) or LB-102 (n=6) treatment for a total of 24 subjects. Four (4) visits will be scheduled for this study: Screening (Visit 1, Days -28 to -1), Check-in (Visit 2, Day 0), Treatment Evaluation (Visit 3, Days 1-9), and Follow-up (Visit 4, Day 15). The study procedures for these visits are presented in

detail in Table 2. Dosage of LB-102 will be based on the PK observed in a minimum of two Part A cohorts. Subjects will receive 2 doses of placebo or LB-102, first dose at 8:00 AM (±1 hour) and second dose approximately 12 hours later, on Days 1-6 and one dose at 8 AM (±1 hour) on Day 7 for a total of 13 oral doses. The first dose on Day 1 will occur following a 12 hour, overnight fast. For each cohort, blood samples for PK will be collected at multiple timepoints starting on Day 1 at pre-dose and at 15, 30, and 45 minutes (±5 min), and 1, 1.5, 2, 3, 4, 6, 8, 12, and 16 hours (±15 min) post first dose. On Days 2-6, blood samples for PK will be collected prior to the first dose. On Day 7 blood samples for PK will be collected pre-dose and at 15, 30, and 45 minutes $(\pm 5 \text{ min})$, and 1, 1.5, 2, 3, 4, 6, 8, 12, 16, 24, 32, and 48 hours $(\pm 15 \text{ min})$ post first dose. Vital signs will be recorded for each subject at Screening, Check-in, Day 1 at pre-dose and at 0.5, 1, 1.5, 2, 4, 6, 8 and 12 hours (±30 min) post first dose on Day 1, at pre-dose and 2 hours (±30 min) post first dose on Days 2-7, 24 and 48 hours (±30 min) post Day 7 dose, and at Follow-up. 12-lead ECG will be done in triplicate at Screening, Check-in, Day 1 at pre-dose and 1, 2, 3, 4, 5, 6, and 8 hours (±30 min) post first dose, prior to first dose on Days 2-7, and on Day 8 (24 hours (±30 min) post-dose Day 7). Clinical labs will be assessed at Screening, Check-in, prior to first dose on Day 4, Day 8, and at Follow-up. HbA1c will be measured in serum at Screening. Prolactin will be measured in serum at Screening, Day 4, Day 9, and Day 15. C-SSRS will be assessed at Screening, Day 4, and Day 8. Subjects will remain in the clinic from Check-in to Discharge on Day 9 for additional safety assessment and then return for a Follow-up Visit on Day 15. Subsequent groups will follow the same study procedures.

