5.4 Selection of Study Population

5.4.1 Inclusion Criteria

A subject will be eligible for inclusion in the study if he or she meets the following criteria:

- Competent to provide informed consent.
- Voluntarily provide informed consent and Health Insurance Portability and Accounting Act (HIPAA) Authorization in accordance with local regulations and governing Institutional Review Board (IRB) requirements prior to any procedures or evaluations performed specifically for the sole purpose of the study.

- Healthy adult male and female subjects between 18 to 55 years of age inclusive at the screening visit.
- Body Mass Index (BMI) \geq 18 and \leq 30 kg/m² at screening visit.
- Subjects must be in good general health as determined by medical history and physical examination with no clinically significant medical findings and no history of significant medical disease (e.g., cardiovascular, pulmonary, renal, etc.) or acute condition with the past 30 days.
- Have normal clinical laboratory test results and ECG, which are not considered to be clinically significant by the Investigator.
- Females participating in the study:
 - a. Either must be of non-childbearing potential [surgically sterilized: hysterectomy, bilateral tubal ligation, salpingectomy, and/or bilateral oophorectomy at least 26 weeks before the Screening Visit] or postmenopausal. Menopause is defined as being amenorrhoeic for at least 2 years with plasma follicle-stimulating hormone (FSH) levels in the post-menopausal range at screening, based on the central laboratory's ranges; OR
 - b. Females of child-bearing potential must have a negative pregnancy test and be not breastfeeding at Screening and use either abstinence or an accepted contraception method during the treatment period and for an additional period of 30 days after the end of investigational treatment. For this study, accepted contraception methods include:
 - condom plus spermicide
 - condom plus diaphragm
 - condom plus cervical cap or female condom
 - hormonal contraceptives
 - intrauterine device
 - partner vasectomy and a use of barrier contraception methods
- If male, subject must be surgically sterile or practicing at least 1 of the following methods of contraception, from initial study drug administration through 90 days after administration of the last dose of study drug:
 - a. Have had a vasectomy (at least 6 months earlier);

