 - b. Use of a double-barrier contraception method, defined as male use of a condom and female use of a barrier method (e.g., contraceptive sponge, spermicidal jelly or cream with or without a diaphragm);
 - c. Partner use of hormonal contraceptives (oral, parenteral, vaginal, or transdermal) for at least 3 months prior to study drug administration;

- d. Partner use of an intrauterine device;
- e. Complete abstinence from sexual intercourse;
- f. Male subjects not practicing complete abstinence must use a condom as a required form of birth control (in addition to at least 1 of the other methods listed above, if desired) in order to protect partners of male participants from exposure to study drug.
- If male, subject must agree to abstain from sperm donation through 90 days after administration of the last dose of investigational drug.

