8.5.7.2 Eliciting and Documenting Adverse Events

The Investigator is responsible for ensuring that all AEs and SAEs are recorded in the CRF and reported to the Medical Monitor. Adverse events will be collected from Check-in (Day 0) through the Day 8 (Cohorts 1-4, Part A; End of Study), or 15 (Cohort 5, Part A or Cohorts 6-8, Part B, respectively; End of Study), or Early Discontinuation Visit.

At each visit, subjects will be asked for any medically related changes in their well-being. They will also be asked if they have had any accidents, used any new medications, or changed concomitant medication regimens (both prescription and over-the-counter medications). In addition to subject observations, AEs will be documented from any data collected on the AE page of the CRF (e.g., clinical laboratory values, physical examination findings, and ECG changes) or other documents that are relevant to subject safety.

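### Section 8.5.8 stops mandatory reporting of partner pregnancies 30 days after the last dose, while the inclusion criteria set a 90-day precaution period for men

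*Protocol*

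**What the plan says.** Section 8.5.8 opens the reporting duty with "If a female subject or the female partner of a male subject becomes pregnant during the course of the study". The second limb of that sentence extends the duty past the end of dosing, to a pregnancy that begins "within 30 days after the last dose of study drug/placebo". One window therefore serves two populations. The rest of the section follows from a reportable pregnancy: the report within 24 hours of notification, the Exposure in Utero form, consent from the woman concerned, and follow-up to the end of the pregnancy where possible.

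The inclusion criteria (Section 5.4.1, repeated in the synopsis) set precaution periods by sex:

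- Women of childbearing potential use contraception or abstinence during treatment and "for an additional period of 30 days after the end of investigational treatment".
- Men are surgically sterile or use contraception "from initial study drug administration through 90 days after administration of the last dose of study drug".
- Separately, for men, the "subject must agree to abstain from sperm donation through 90 days after administration of the last dose of investigational drug".

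The condom item in the male list gives a reason: "in order to protect partners of male participants from exposure to study drug".

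**The concern.** The 30 days in Section 8.5.8 equal the female precaution period. The same figure is applied to partners of male subjects, for whom the related precaution lasts 90 days. The protocol thus asks men to take precautions for three months, partly for the sake of their partners, yet requires the site to report a failure of those precautions only if conception occurs in the first month.

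What is at stake is the record of pregnancies and their outcomes. According to Section 3.4 the sponsor had run no earlier human study of LB-102, so this trial is where such information would first arise. Outside the window the protocol does not forbid a report, but it requires none, and a voluntary report is not systematic capture.

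**Working it through.** No sample size, power or error rate is involved. The check sets the protocol's own time windows side by side.

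**Inputs**

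- Reporting window, female subjects and partners: 30 days after last dose (Section 8.5.8).
- Female precaution period: 30 days after end of treatment (Section 5.4.1).
- Male precaution period, contraception and sperm donation: 90 days after last dose (Section 5.4.1).
- Last dose: Day 1 in Part A. In Part B it is Day 7: "one dose at 8 AM (±1 hour) on Day 7 for a total of 13 oral doses" (Section 5.1).
- Last scheduled visit: Day 8 (Cohorts 1-4), Day 15 (Cohort 5), Day 15 (Part B).

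**Step 1: precaution minus reporting**

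- Women: 30 − 30 = 0 days uncovered.
- Men's partners: 90 − 30 = 60 days uncovered, namely days 31 to 90 after the last dose.

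**Step 2: does the wording on the course of the study extend the window?** Days from last dose to last scheduled visit:

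- Cohorts 1-4: 8 − 1 = 7
- Cohort 5: 15 − 1 = 14
- Part B: 15 − 7 = 8

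All are below 30. For an individual subject the 30-day limit is therefore the outer bound, and the phrase adds nothing.

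**Step 3: does any other section close the gap?**

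- Section 8.5.7.1 asks that the Medical Monitor be told of a new pregnancy in a dosed subject. It does not mention partners.
- Section 8.5.7.2: "Adverse events will be collected from Check-in (Day 0) through the Day 8" for Cohorts 1-4, and through Day 15 for the other cohorts.
- Section 8.5.7.7 caps adverse event follow-up at 30 days after dosing.

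None of these reaches a partner pregnancy after day 30.

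**Step 4: which pregnancies are affected?** Section 8.5.8 turns on when the woman becomes pregnant, and the 24-hour clock runs from when the site learns of it. A conception inside 30 days that is discovered later remains reportable. The gap concerns conceptions on days 31 to 90 only.

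**Step 5: reach.** Appendix 1 describes the Part A dose levels in the past tense and reports Cohort 5 results through the Day 15 visit. A change would therefore mainly affect Part B: 3 cohorts × 8 = 24 subjects, of whom 3 × 6 = 18 receive LB-102. The number of men among them is not given.

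**The case against.** **The two rules do not conflict.** One binds the subject and the other the investigator, both can be followed at once, and nothing says the periods must be equal. This stands as far as it goes: it is a mismatch, not a logical contradiction. But the rule is stated and not left open, it matches the precaution period for one sex and not the other, and no reason for the difference is given.

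**The protocol never declares a 90-day risk.** A reader might infer that it does. It sets a 90-day precaution period. The stated purpose of protecting partners sits in the condom item only, and is not given for the sperm-donation rule. The stronger reading is therefore not supported.

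**Drug will be gone by day 30.** Appendix 1 gives mean terminal half-lives from 12.311 h to 14.656 h. Thirty days is 720 h, and 720 / 14.656 ≈ 49 to 720 / 12.311 ≈ 58 half-lives, so residual circulating drug is negligible on these single-dose figures; multiple-dose data are not yet available. This weakens residual exposure as a reason for concern. It does not remove the mismatch, because the same version carries these data and still keeps 90 days for men and 30 for women.

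**Safety is the primary objective, but partner pregnancy is not part of it.** This stands. The objective is safety and tolerability against placebo, and neither the listed safety assessments nor the safety analyses include partner pregnancies.

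**The course of the study might mean the whole trial.** The phrase is undefined. On that reading the gap shrinks for early cohorts but stays largest for the last, so coverage would depend on cohort order. Adverse event collection that ends subject by subject favours the individual reading.

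**Conclusion.** The point holds as a mismatch in safety capture. A partner pregnancy conceived on days 31 to 90 after the last dose lies inside the male precaution period the protocol sets, yet need not be reported or followed to outcome. The uncovered span is 60 days for partners and none for female subjects.

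This rests on two assumptions: that the course of the study refers to the subject's own participation, and that the reporting duty is meant to track the precautions, as it does for women.

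Two further inferences should not be drawn. Sixty of 90 days is 67% of the calendar period, not 67% of events: a missed case needs a conception despite the required precautions, the number of men is not stated, and no expected count can be derived. Nor are the primary objective or any analysis compromised, since no endpoint, escalation decision or planned summary uses partner pregnancies. It is worth correcting because the clause is specific and the change small, but the practical reach is mainly Part B.

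**What to change.** Reconcile Section 8.5.8 with the male inclusion criteria. State the reporting window separately for female subjects and for partners of male subjects, so that the partner window covers whatever male precaution period the protocol sets. Ask male subjects to tell the site of a partner pregnancy in that period. Defining the course of the study in the same sentence would remove the remaining ambiguity. The review takes no position on how long the male precaution period itself should be.

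The cost is more than a phrase. Section 12.3 requires IRB approval of an amendment before it is implemented. Scheduled contact ends 7 to 14 days after the last dose, so later capture depends on subjects coming forward. No visit, sample or analysis has to change.

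If the sponsor prefers to keep 30 days for partners, the protocol should say why reporting ends before the male precaution period does.

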8.5.9 Laboratory Safety Assessments

Samples for the following laboratory tests will be collected at the time points specified in the Schedule of Events (Table 1 and Table 2). The blood samples for serum chemistry tests will be collected following a minimum 8-hour fast.

Given that it may be possible for individuals who have access to prolactin data to presume which subjects received LB-102 and which subjects received placebo, prolactin data will be de-identified prior to Investigator review during the Treatment Period. Likewise, de-identified prolactin data will be provided to the SRC members for review prior to each dose escalation meeting. Subject IDs will be disclosed for clinical evaluation for prolactin levels that are > 100 ng/mL.

Consists of complete blood count (hemoglobin, hematocrit, white Hematology:

blood cell count with differential, red blood cell count, and platelet

count)

Includes blood urea nitrogen, creatinine, total bilirubin, alkaline

phosphatase, aspartate aminotransferase (serum glutamic-

Serum chemistry: oxaloacetic transaminase), alanine aminotransferase (serum

glutamic pyruvic transaminase), glucose, HbA1c*, albumin,

prolactin, and total protein

Includes pH, specific gravity, protein, glucose, ketones, bilirubin,

blood, nitrites, leukocytes, urobilinogen, microscopic urine analysis Urinalysis:

if dipstick positive

Serum* and Urine

pregnancy test:

Conducted for females of childbearing potential only

FSH Postmenopausal females (at screening only)

Cocaine, amphetamine, phencyclidine, benzodiazepines, opiates, Urine Drug Screen:

and marijuana.

8.5.10 Vital Signs

Resting vital signs, including blood pressure, heart rate, respiratory rate and temperature will be measured after the subject has been in a seated position for at least 5 minutes at the time points specified in the schedule of events (Table 1 and Table 2).

Blood pressure or heart rate outside of the recommended ranges will be rechecked if considered clinically significant by the Investigator.

8.5.11 Electrocardiogram

A 12-lead ECG will be performed after the subject has been in supine resting for at least 10 minutes, and at the following times:

Part A: Screening, Check-in, Day at pre-dose and 1, 2, 3, 4, 5, 6, 8, and 24 hours (±30 min) post-dose. ECG will be measured once at each time point for Cohorts 1-4 and in triplicate for Cohort 5.

Part B: Screening, Check-in, Day 1 Pre-dose and 1, 2, 3, 4, 5, 6, and 8 hours (±30 min) post-dose, prior to the first dose on Days 2-7, and Day 8 (24 hours (±30 min) post Day 7 dose). ECG will be measured in triplicate at each time point.

^{*}Serum for pregnancy test and HbA1c assessment are only required at Screening.

8.5.12 Physical Examination

A standard physical examination will be performed at Screening, Check-in, Day 2, and Follow-up in Part A and at Screening, Check-in, Days 2, 4, and 8, and Follow-up in Part B. The examination will include assessment of skin, head, ears, eyes, nose, throat, neck, thyroid, lungs, heart, cardiovascular, abdomen, lymph nodes, neurological (with a particular focus on monitoring for manifestations of Extrapyramidal Symptoms), and musculoskeletal system/extremities. Interim physical examinations will be performed at the Investigator's discretion if necessary, to evaluate AEs or clinical laboratory abnormalities.

Height and weight will be measured at Screening and only weight will be measured again at Follow-up for Part A and B.

8.5.13 Columbia-Suicide Severity Rating Scale (C-SSRS)

The baseline C-SSRS will be completed at Screening (both SAD and MAD) and at Day 3 (SAD), Day 4 and Day 8 or early termination (MAD only). The C-SSRS was developed by researchers at Columbia University as a tool to help systematically assess suicidal ideation and behavior during participation in a clinical trial of centrally acting drugs. The C-SSRS is composed of three questions addressing suicidal behavior and five questions addressing suicidal ideation, with sub questions assessing the severity.

The tool is administered via interview with the subject (by a trained operator/interviewer). All attempts will be made to use the same interviewer for the same subject throughout the study.

In the event the subject has a positive and significant finding for depression and/or suicidal ideation upon assessment at screening or Day 3 (SAD only) Day 4 or Day 8 (MAD only) the following will occur, at the discretion of the Principal Investigator and Medical Monitor:

Screening positive and significant findings (SAD and MAD):

• For positive and significant findings at Screening the subject will be considered a screen fail according to exclusion criterion 6 (Section 5.4.2). Proper follow up will be based on the severity of the symptoms.

Day 3 (SAD) or Day 4 or Day 8 positive and significant findings (MAD only)

- The subject will be continuously monitored at the site by qualified personnel, including one-on-one observation, as needed
- The subject will be re-evaluated on an as-needed basis by the Investigator
- Dosing will be interrupted or discontinued
- Psychiatric consultation may be pursued based on the severity of symptoms and at the discretion of the Principal Investigator

8.5.14 Concomitant Medications

Concomitant medications will be reviewed and documented each day during the study.

8.5.15 Sample Collection and Processing

Details of sample process will be provided in the lab manual

8.5.16 Sample Storage

Plasma samples will be stored according to the lab manual.

8.5.17 Sample Shipment

- Prior to shipment, the samples will be appropriately packed into a styrofoam cooler containing dry ice.
- Sufficient dry ice will be added to ensure that the samples will remain frozen for at least 24 hours for local shipments and for at least 72 hours for remote shipments.
- Samples will be shipped in two aliquots. The second set will be shipped once the status of the first set has been verified.
- The site staff will maintain an inventory of the samples that are to be shipped to the bioanalytical laboratory, including the name of the study drug, protocol number, and the subject numbers and samples included in the shipment. A copy of the inventory will accompany the frozen PK samples.
- The samples will be tracked to ensure arrival in a safe and timely manner.

9. STATISTICAL METHODS

9.1 General Considerations

A Statistical Analysis Plan (SAP) that describes the details of the analyses to be conducted will be finalized before database lock.

9.2 Analysis Populations

The following analysis populations are planned:

• Safety Population: All subjects who receive study drug.

9.3 Statistical Analyses

Continuous variables will be summarized by treatment using descriptive statistics (n, mean, median, standard deviation, minimum, and maximum). For categorical variables, frequencies and percentages will be presented by treatment. Baseline is defined as the last observation prior to initiation of study medication. Details of the statistical analyses will be provided in the Statistical Analysis Plan which will be finalized prior to database lock.

9.3.1 Subject Disposition and Demographic Characteristics

Subject disposition will include the number of subjects who enroll in the study and the number and percentage of subjects included in each analysis population by treatment. The frequency and percentage of subjects who withdraw or discontinue from the study, along with the reason for withdrawal or discontinuation, will be summarized by treatment.

Demographics and baseline characteristics, including age, sex, race, weight, height and BMI, will be summarized by treatment for the Safety Population.

